8.11 Establishment of diagnosis

- 1. Each lesion to be evaluated for efficacy will be aspirated and/or scraped and/or biopsied.
- 2. Proof of infection will include the demonstration of motile promastigotes in aspirate cultures or microscopic identification of Leishmania amastigotes (by DifQuiK or Giemsa staining) in material obtained from lesions.

8.12 Definition of responses using clinical criteria

Lesions will be measured in two perpendicular directions, and photographs will be taken, prior to therapy, at the end of therapy, and at 50 days, 3 months, (D1 being the first day of treatment). Physically identifying features if present will be hidden in photographs. Patients will be identified by initials and not by name. Because the trial can't be blinded, clinical evaluation at D50 will be performed by an independent physician ([name]) unaware of the occlusion process. Patients will be asked not to inform the evaluating physician if the lesion was covered.

Efficacy will be evaluated in terms of percentage of patients cured or improved at D50 (D1 is the first day of treatment) with no relapse during 3 months post-treatment follow-up.

1. Cure: 100% reepithelialization without relapse by 3

months.

2. Clinical improvement: $\geq 50\%$ but $\leq 100\%$ reepitheliazation compared to pre-

treatment lesion size at day 50 (\pm 7 days).

3. Clinical failure: a. Lack of clinical improvement at day 50 (\pm 7 days)

after the beginning of treatment.

b. Relapse that is enlargement of the lesion compared to the previous measurement at any time after day 50

 $(\pm 7 \text{ days}).$

c. Not demonstrating complete clinical response by 3

months (i.e. not being cured by 3 months).

8.13 Definition of cure

Determination of cure will be based on clinical criteria. A lesion (ulcer) will be defined as cured if it has undergone a complete clinical response.

8.14 Criteria for Early Withdrawal from the Study

Any one of the following criteria will be considered sufficient to cause the withdrawal of the patient from the study.

- 1. Adverse effects (particularly those listed in section 7.10.2) reported by the patient or medical personnel that in the opinion of the principal investigator pose a serious risk to the patient.
- 2. Clinical failure or relapse. Patients who require re-treatment for failure or relapse will be removed from the protocol and treated with the standard of care, probably 0.5 3.0 ml of Glucantime intralesionaly once per week for a maximum of 5 weeks or in case of

multiple lesions (n≥4) Glucantime at 20 mg SbV/kg /day for a maximum of 20 days) or the attending physician drug of choice.

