2.0 BACKGROUND

An analysis of the data from the recent WR 279,396 study (HSRRB Log # A-9768.1) indicates that by day 50, cure rate was 91.8% in the treatment group and 73.2% in controls ($x^2 = 5.60$, p= 0.017) and complete cure response was 95.8% among the former versus 75% among the latter ($x^2 = 8.04$, p= 0.004). The global healing rate is already much higher than the previous (placebo) 25% healing rate in the same area using the same evaluation criteria (Ben [name] 95). The occlusive dressing used during the ongoing trial may have positively influenced the healing rate, by enhancing drug diffusion into the deep dermis and accelerating the reepithelialization process. The practicability of polyurethane adhesive dressings was not perfect however. Local reactions (mild pain, redness and edema) was noticed among 22 patients (11 among the treatment group (22.4%) and 11 among controls (28.6%), NS. Although no patient stopped drug applications, topical treatment might be improved by simplifying the regimen. WR 279,396 without occlusion was superior to placebo in a Colombian Phase 2 study (Soto 02) making it the reference schedule. No tolerance problems were observed in this trial.

The Office of the Surgeon General, United Sates Army represented by USAMMDA holds the IND for WR 279,396 and will continue the development of the product through a commercial pharmaceutical partner in order to obtain licensure by the FDA.

Thus, this Phase 2 study is to determine whether WR 279,396 with occlusion (a polyurethane dressing) is more effective than WR 279,396 without occlusion. Furthermore, a consistent difference in efficacy will be necessary to justify the relatively lower tolerance and higher cost of an occlusive dressing, and this study will help determine which form of dressing should be used.

Extensive objective and subjective local tolerance data will also be captured during this trial, as well as surrogate markers (parasite loads and aminoglycosides concentration in the deep dermis) that may help to determine the optimal number and duration of treatments. Finally, this study, which will be conducted from October 2005 through March 2007, will bridge the time gap between the 2004 Phase 2 study and the planned 2006 Phase 3 study. This will serve to keep the clinical team in Tunisia active and ready to start the next trial should that study be necessary.

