8.15 Concomitant medications

If concomitant medical problems occur, medications that are possibly effective against cutaneous leishmaniasis (antimony, amphotericin B, pentamidine, injectable paromomycin, fluconazole, ketoconazole, allopurinol) will only be used as a measure of last resort and this patient will be withdrawn from the protocol.

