9.0 SAMPLE SIZE AND DATA ANALYSIS

9.1 Sample size calculation

If the cure rate in the WR 279,396 without occlusion group is assumed to be $60\%^1$, and we desire at least a 35% improvement in the cure rate due to occlusion, for alpha=0.05 (1-sided) and beta=0.2, 20 patients under WR 279,396 without occlusion plus 20 patients WR 279,396 with occlusion (40 patients) are required for 1:1 allocation.

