9.3 Treatment randomization codes

The study will be randomized 1:1 occlusion/non occlusion. The randomization list will be generated by the Department of Epidemiology of Institut Pasteur of Tunis using a sequential numbers from 1 to 50.

¹ In Colombia, WR279396 without occlusion gave a 60% cure rate (30% above the placebo cure rate).

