Appendix A (Adverse or Unexpected Event Determination – Side Effects and Grades)

1. Cutaneous adverse reactions (i) on the edge of lesion (ii) on surrounding healthy skin [grade erythema separately from edema]

Grade 0: no reaction (no erythema or edema)

Grade 1: mild reaction (barely perceptible erythema or edema)

Grade 2: moderate reaction (well defined erythema or edema)

Grade 3: Severe reaction (very red erythema with raised > 2mm edema)

Grade 4: life threatening reaction (exfoliative dermatitis)

NOTE: Grade 3 reactions require immediate notification to Medical Monitor. Grade 4 reactions require immediate termination of treatment and ADVERSE EVENT NOTIFICATION.

2. Abnormal clinical laboratory values (DAIDS/NIH scale):

Parameter (units)	Grade 1	Grade 2	Grade 3	Grade 4
Creatinine (xULN)	>1-1.5	>1.5-3	>3-6	>6
AST/ALT (XULN)	1.25-2.5	>2.5-5	>5-10	>10
WBC (1,000/mm3)	1000-1500	750-999	500-749	< 500
PLT (1,000/mm3)	75-99	50-74	20-49	< 20
HGB (g/dL)	8-9.4	7-7.9	6.5-6.9	< 6.5

NOTE: Grade 2 require immediate notification to Medical Monitor.

Grade 3 and 4 reactions require immediate termination of treatment.

Grade 2, 3 and 4 laboratory values require evaluation of the volunteer. If the laboratory abnormality reflects clinically significant pathology, an ADVERSE EVENT report will be fill out and notification will occur.

3. Miscellaneous (associated with drug administration):

Pain:

Grade 0: none (feels no pain)

Grade 1: mild pain (does not interfere with daily activity)

Grade 2: moderate pain (interferes with daily activity)

Grade 3: severe pain (daily activities are interrupted)

NOTE: Grade 2 reactions require immediate notification to Medical Monitor. Grade 3 reactions require immediate termination of treatment and ADVERSE EVENT NOTIFICATION.

Vertigo:

Grade 0: none (feels no vertigo)

Grade 1: mild vertigo (does not interfere with daily activities)

Grade 2: moderate vertigo (interferes with daily activity)

Grade 3: severe vertigo (daily activities are interrupted)

NOTE: Grade 2 reactions require immediate notification to Medical Monitor. Grade 3 reactions require immediate termination of treatment and ADVERSE EVENT NOTIFICATION.

Tinnitus:

Grade 0: none (feels no ringing/buzzing/roaring etc.)

Grade 1: mild tinnitus (does not interfere with daily activities)

Grade 2: moderate tinnitus (interferes with daily activities)

Grade 3: severe tinnitus (daily activities are interrupted)

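### Safety withdrawal in 8.14, 8.15 and 12.0 means leaving the study, with no rule that keeps the D50 and D90 lesion assessments; the likely bias is small, but the missing outcomes cannot be recovered

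*Protocol*

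**What the plan says.** Section 8.14 is about leaving the study: "Any one of the following criteria will be considered sufficient to cause the withdrawal of the patient from the study". Its first criterion is adverse effects, limited to those that the principal investigator considers a serious risk. Section 8.15 says of drugs with possible antileishmanial activity given for concomitant problems that they "will only be used as a measure of last resort and this patient will be withdrawn from the protocol". Section 12.0 (Ethics) adds withdrawal from the research for health reasons.

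Appendix A uses different terms. For pain, vertigo and tinnitus, "Grade 3 reactions require immediate termination of treatment and ADVERSE EVENT NOTIFICATION". It ends treatment and does not mention leaving the study.

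The timetable in 8.17 has lesion measurements at D50 and D90 and no early-withdrawal visit. Section 8.12 provides an independent evaluator at D50 who is not told about occlusion. Section 9.4 omits subjects lost to follow-up before D50 from the analysis, and otherwise says that the investigators will try to obtain missing data.

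On tolerance, section 2.0 says that a consistent gain in efficacy is needed to "justify the relatively lower tolerance and higher cost of an occlusive dressing".

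**The concern.** The protocol does not keep stopping the drug and leaving the study apart. A patient withdrawn under 8.14, 8.15 or 12.0 before D50 has no lesion assessment provided for. If the withdrawal is treated as loss to follow-up, 9.4 takes the patient out of the primary comparison.

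Such a loss would not be random if the reason for withdrawal is related to treatment and patients whose course is cut short cure less often. The protocol expects lower tolerance with occlusion, and section 2.0 suggests that occlusion may increase drug diffusion into the dermis. More of any such losses could therefore fall in the occlusion arm, which would flatter occlusion. With 24 patients per arm, each patient is 1/24 = 4.2 percentage points.

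This is a matter of data collection. An analysis plan can change how a missing outcome is handled, but it cannot supply a D50 examination that was not done.

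**Working it through.** **1. The passages side by side**

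| Place | Trigger | Consequence stated | Lesion visits afterwards |
|---|---|---|---|
| 8.14, item 1 | adverse effects judged a serious risk | leaves the study | not stated |
| 8.15 | listed drugs given as a last resort | leaves the protocol | not stated |
| 12.0 | health conditions making participation dangerous or detrimental | leaves the research | not stated |
| Appendix A | high-grade reactions or laboratory values | treatment ends | not stated; nothing removes the patient from 8.17 |
| 9.4 | lost before D50 | omitted from analysis | – |

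Item 2 of 8.14 (failure or relapse) is a lesser problem, because 8.12 defines those outcomes at D50 or later and they are known when the patient leaves.

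**2. The plan's sample size**

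Inputs from 9.1 and its footnote: "In Colombia, WR279396 without occlusion gave a 60% cure rate"; "we desire at least a 35% improvement in the cure rate due to occlusion", read as 60% v 95%; "for alpha=0.05 (1-sided) and beta=0.2". The stated result is 20 per arm. Exact power of the one-sided Fisher test at 20 per arm is 80.8%, so the figure reproduces. At the planned 24 per arm it is 89.0%.

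If k occlusion patients are excluded, power is 86.2% (k=1), 86.9% (k=2), 84.7% (k=3) and 84.6% (k=4). It is not monotone because the test is discrete. Loss of power is minor; the issue is bias.

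**3. How many withdrawals are plausible**

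The protocol gives no withdrawal rate. Section 2.0 says that nobody stopped drug in the earlier occluded trial, which reports 49 active patients. The one-sided 95% upper bound is 1 − 0.05^(1/49) = 5.9%, and 24 × 0.0593 = 1.4 patients. A plausible k is 0 to 1.

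**4. Bias from excluding k occlusion patients**

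Assumptions: true cure is 60% in both arms, all k would have failed, and none is lost from the other arm. Observed occlusion rate = (24 × 0.60)/(24 − k) = 14.4/(24 − k).

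| k | Observed rate | Bias (points) | One-sided Fisher type I error |
|---|---|---|---|
| 0 | 60.0% | 0 | 2.8% |
| 1 | 62.6% | +2.6 | 4.1% |
| 2 | 65.5% | +5.5 | 5.8% |
| 3 | 68.6% | +8.6 | 8.9% |
| 4 | 72.0% | +12.0 | 13.2% |

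If the excluded patients respond like the rest, the rate is (14.4 − 0.6k)/(24 − k) = 60% and the bias is zero for every k.

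**5. Effect on a single result**

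Take 18 cures under occlusion and 14/24 without, all excluded patients being failures. One-sided Fisher p is 0.179 (18/24), 0.124 (18/23), 0.079 (18/22), 0.044 (18/21) and 0.020 (18/20). At the plausible k of 0 to 1, p moves from 0.179 to 0.124.

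**The case against.** Several stronger readings are tempting, and the protocol does not support them.

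- **Any adverse effect removes the patient.** It does not. Section 8.14 requires a serious risk in the investigator's judgement. It points particularly to a section 7.10.2 that does not exist. If 8.10.2 is meant, those are creatinine, hearing and balance findings, not local skin reactions. Grade 3 erythema or edema in Appendix A requires only notification.
- **The outcomes are never measured.** This would be an inference from silence. Section 17.2.3 continues contact for adverse events, 9.4 promises an effort to recover missing data, and 8.8 has each patient followed for three further months. A patient withdrawn after D50 already has the D50 result.
- **More losses will occur under occlusion.** This is possible but not shown. In the earlier occluded trial local toxicity was grade 1 and lasted 1–3 days (6.5.4.2), and section 4.0 expects fewer dressing-related events with once-daily use. The unoccluded Colombian trial reports grade 1 pain in 55% of active patients, against 22.4% with local reactions under occlusion. These are separate trials with different measures.
- **Exclusions could turn a null result significant.** The p = 0.044 case needs three exclusions, all failures, and none in the other arm. Occluded placebo patients had 73.2% cure at D50; at that rate three failures out of three have probability 0.268³, about 2%. At the 20–44% spontaneous cure in 6.1.1 it is 0.56³ to 0.80³, or 18% to 51%. Section 9.2 also counts improved lesions as response, which makes failure less likely still.

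These points stand, and they limit the size and certainty of the bias. They do not supply a rule for lesion follow-up after withdrawal or reconcile 8.14, 8.15 and 12.0 with Appendix A. Adverse-event contact is not a lesion assessment, and a best effort is not a scheduled visit. It is also fair to say that a lesion seen after another antileishmanial drug no longer measures WR 279,396 alone. How to count it needs stating, but that is no reason not to examine it.

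**Conclusion.** The point holds as a gap and an inconsistency in the protocol. Three sections equate withdrawal with leaving the study, Appendix A speaks only of ending treatment, no passage secures the D50 and D90 lesion assessments, and 9.4 can then drop the patient. The resulting bias could favour occlusion, but neither its direction nor its occurrence is established.

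The plausible size is 0 to 1 occlusion patient, or 0 to about 2.6 percentage points, with type I error at most about 4.1% against a nominal 5%. This rests on 0 of 49 stopping in the earlier trial carrying over to this one, 60% true cure in both arms, and the worst case that the excluded patient would have failed. The 49 come from the 90 of 92 randomised patients who completed follow-up; the arm and reasons of the other two are not given. The case for changing the text is that the change is nearly free and a missed outcome cannot be recovered, not that a large bias is expected.

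**What to change.** Reconcile 8.14, 8.15, 12.0 and Appendix A so that stopping study drug and leaving the study are separate events. State that patients who stop drug or receive other antileishmanial treatment keep the planned masked D50 evaluation and the D90 visit unless they withdraw consent. Record the date and reason of stopping, and keep these patients in their randomised arm. Make clear in 9.4 that stopping drug is not loss to follow-up, and correct the cross-reference to 7.10.2.

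When treatment stops and what rescue is given stay as the protocol has them. The cost is protocol wording, since the visits and the evaluator are already planned for every patient. The one added task is to state how lesions examined after other antileishmanial treatment are counted.

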8.15 Concomitant medications

If concomitant medical problems occur, medications that are possibly effective against cutaneous leishmaniasis (antimony, amphotericin B, pentamidine, injectable paromomycin, fluconazole, ketoconazole, allopurinol) will only be used as a measure of last resort and this patient will be withdrawn from the protocol.

8.16 Departure from the protocol

Additional tests/procedures may be performed for clinical management at the discretion of the attending physician.

Notification that additional tests/procedures are being performed or of desired protocol amendments will be sent to the responsible IRB(s), Clinical Monitors, Study Coordinator, USAMMDA. In addition, departures from the approved protocol will be noted and reported to the IRBs in a timely manner.

Changes to the approved protocol will be approved by the Tunisian IRB and by the Human Subjects Research Review Board (HSRRB) prior to implementation. Changes intended to eliminate an apparent immediate hazard to a subject will be immediately implemented provided the reviewing IRBs are notified.

Any departures from the protocol that significantly affect the integrity of the study of the safety and welfare of subjects will be promptly reported to the HSRRB.

8.17 Procedural timetable

	Procedure	Therapy Period (days)	Follow-up (#Days)
--	-----------	-----------------------	-------------------

	0/1	10	20	50±7	90±7
Informed Consent	X				
Demographic Details	X				
Medical History	X				
History of Leishmaniasis	X				
Physical Exam	X				
Dermatology Exam	X				
Hearing Test	X	X	X		
Romberg Test	X	X	X		
CBC (WBC,platelets, Hgb)	X				
AST or ALT	X				
Serum Creatinine	X	X	X		
Glucose, Na, K	X				
Pregnancy Test	X				
Urinalysis	X		X		
Measure ulcer and induration	X	X	X	X	X
Clinical Evaluation of Lesion	X	X	X	X	X
Photograph Lesion	X	X	X	X	X
Parasitologic Tests	X				
Cutaneous Biopsy	X	X			
Aminoglycoside concentration	X	X			
Parasite load	X	X			
Leishmania Culture (Microdilution	X	X			
Test)					
Parasite load by DNA and RNA	X	X			
techniques					
Entrance Exam and Lab Test	X				
Check List					

Drug Therapy	Days 1 through 20
Local Toxicity	Days 1 through 20

9.0 SAMPLE SIZE AND DATA ANALYSIS

9.1 Sample size calculation

If the cure rate in the WR 279,396 without occlusion group is assumed to be $60\%^1$, and we desire at least a 35% improvement in the cure rate due to occlusion, for alpha=0.05 (1-sided) and beta=0.2, 20 patients under WR 279,396 without occlusion plus 20 patients WR 279,396 with occlusion (40 patients) are required for 1:1 allocation.

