1.0 GENERAL INFORMATION

50,098/ IND/Date of submission

CPP Protocol #/Date Approved No. / (mm/dd/yy) Department of Defense (DOD) Sponsor

Office of The Surgeon General of the Army

Commander Sponsor Representative:

U.S. Army Medical Materiel Development Activity

(USAMMDA) [name]

[name]

[contact]/[name]

[contact]

Institut Pasteur, Tunisia Principal Investigator:

[name] [name], PhD [contact] [contact]-

[name]

Subinvestigators: Institute Pasteur, Tunisia

[name] [contact] [contact]-

[name]

Scientific Expert and Consultant: Pôle de Recherche Biomédicale, Centre Médical de

[name], PhD l'Institut Pasteur, Institut Pasteur,

[name]

[contact] [contact]

Tripler Army Medical Center Study Coordinator and Consultant:

[name] Department of Clinical Investigation

Honolulu, Hawaii

[contact]

Coordinator and logistical support

Pôle de Recherche Biomédicale du Centre Médical [name]

de l'Institut Pasteur, Institut Pasteur,

[name] [contact] [contact]-

[name]

Monitor: **USAMMDA**

Ft. Detrick, MD

[contact]

[name], R.N.

Medical Monitor Institut Pasteur de Tunis

[name] [name] [name],

Tunisia

[contact]

Protocol: A-9768.2 Ver 9.0 14 March 2010 Phase 2 WR 279,396 Study in Tunisia

Office of The Surgeon General Department of the Army

Study Location: Tunis, Tunisia

Institut Pasteur de Tunis

Institute Pasteur, Tunis, Tunisia [name],

Tunisia

Study Duration: 17 Months

Anticipated Start Up Date: November 2005

Required No. of Volunteers: 40

TABLE OF CONTENTS

1.0	GENERAL INFORMATION	2
2.0	BACKGROUND	6
3.0	STUDY SUMMARY	6
4.0	STUDY OBJECTIVES	7
5.0	FACILITIES TO BE USED	8
6.0	BACKGROUND OF LEISHMANIASIS	8
	6.1 Natural history and drug treatment of Old World cutaneous leishmaniasis	8
	6.1.1 Old World cutaneous leishmaniasis	8
	6.2 Present topical agents	10
	6.3 WR 279,396 Preclinical Efficacy	11

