6.4 Clinical Efficacy of WR 279,396

6.4.1 Summary of Phase 2 studies

In 1999, a pilot phase 2 study was conducted in Colombia. This clinical study was a randomized, double blind trial of WR 279,396 compared to placebo (the cream base of WR 279,396), each administered twice-a-day for 20 days without occlusion.

In the active group in Colombia (in which WR 279,396 was applied without an occlusive dressing), 33 of 51 evaluable lesions cured (66%) at D50 and 5 lesions were non-evaluable (59% in intent-to-treat analysis). In the placebo group, 4 of 12 evaluable lesions cured (33%) at D50, and 5 lesions were non-evaluable.

There was no statistical difference between the pre-treatment sizes for cured vs failed lesions in WR 279396 patients (p = 0.7) nor in placebo patients (p = 0.8).

The 36 lesions that were treated with WR 279,396 were recognized as cured at the end of therapy on day 20 (20 lesions), at the first follow up on day 45 (13 lesions), and on day 90 (3 lesions). The 6 placebo lesions that cured were recognized on day 20 (1 lesion), day 45 (3 lesions), and day 90 (2 lesions). The mean cure time of 35 days for cured WR 279396 lesions was statistically different (p = 0.04) from the mean cure time of cured placebo lesions (56 days).

In 2003-2004, a Phase 2 study was conduced in Paris & Tunisia, Old World cutaneous leishmaniasis. 92 subjects were randomly assigned to treatment of which 90 subjects (80

from Tunisia and 10 from Paris) achieved all the follow-up period. Patients allocated treatment (n= 49) and placebo (n= 41) were similar for prognostic factors at inclusion (socio-demographic variables and clinical features of lesion). Each lesion was treated twice daily. Lesions were measured at the end of therapy, and at 50, 80 and 180 days after the institution of treatment. Cure rate at day 50 was 91.8% in the treatment group and 73.2% in controls ($x^2 = 5.60$, p= 0.017) and complete cure response was 95.8% among the former versus 75% among the latter ($x^2 = 8.04$, p= 0.004).

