8.0 EXPERIMENTAL PLAN

8.1 Trial Design

Fortyeight (48) patients of Old World cutaneous leishmaniasis will be randomly allocated to WR 279,396 treatment once-a-day for 20 days with occlusion (24 patients), without occlusion (24 patients). Patients not cured will be rescued with a conventional treatment accepted in Tunisia as determined by the primary care physician. The active ingredients of WR 279,396 are two aminoglycosides – paromomycin sulphate (15%) and gentamicin sulphate (0.5%) – in a base (AQIC).

Efficacy will be evaluated in terms of the number of lesions cured i.e. percentage of subjects cured at D50 (D1 is the first day of treatment) with no relapse during 3 months post-treatment follow-up. Cure is defined as 100% reepitheliazation without relapse by 3 months. Clinical improvement is defined as \geq 50% but \leq 100% reepitheliazation compared to pre-treatment lesion size at day 50 (\pm 7 days). Lack of clinical improvement at day 50 (\pm 7 days), relapse that is enlargement of the lesion compared to the previous measurement at any time after day 50 (\pm 7 days), or not demonstrating complete clinical response by 3 months will be a clinical failure. Time to cure will also be determined. Toxicity will be evaluated by local adverse reactions, and by laboratory signs of systemic events.

Induration of the lesion, as measured by the ball-pen technique, will be measured at the same time as lesion size. A photograph will be taken concurrently with these measurements to document the procedure and provide a visual record of the induration measurement and lesion size.

In addition to the clinical evaluation of the CL lesions, the following parameters/clinical healing surrogates will be investigated: (a) parasites loads will be determined in superficial and deep lesion dermis at D0 and D10. The mean parasite log-reduction ratio (log parasite load at D10/log parasite load at D0) in each group will be compared; (b) aminoglycoside concentrations in superficial and deep infiltrated dermis in each group will be compared.

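### The required number is given as both 40 and 48, and the 80% power in 9.1 depends on two borrowed cure rates and on an endpoint that 9.2 does not test

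*Protocol*

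**What the plan says.** **Number of patients.** Section 1.0 states "Required No. of Volunteers: 40", and 9.1 arrives at the same total, 20 per arm. Section 8.1 states "Fortyeight (48) patients of Old World cutaneous leishmaniasis will be randomly allocated", 24 to each arm; 3.0 and 8.4 also give 48. Section 9.3 describes a 1:1 randomisation list "using a sequential numbers from 1 to 50".

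**Calculation.** Section 9.1 takes 60% as the cure rate without occlusion and continues: "we desire at least a 35% improvement in the cure rate due to occlusion, for alpha=0.05 (1-sided) and beta=0.2". The footnote to 9.1 gives the source of the 60%: "In Colombia, WR279396 without occlusion gave a 60% cure rate (30% above the placebo cure rate".

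**Background rates.** For the Colombian active arm, treated twice daily without occlusion, 6.4.1 reports "33 of 51 evaluable lesions cured (66%) at D50 and 5 lesions were non-evaluable (59% in intent-to-treat analysis". For the Old World study, treated twice daily with occlusion (6.5.4.2), 2.0 reports that "by day 50, cure rate was 91.8% in the treatment group and 73.2% in controls". It also reports a complete cure response of 95.8% against 75%.

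**Analysis.** Section 9.2 names Fisher's exact test without a side. It defines the primary criterion as the percentage of patients whose lesions are all cured or improved at day 50. Section 9.4 leaves patients lost before day 50 out of the analysis.

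**The concern.** Two sections require 40 patients and three plan 48. No dropout allowance or other text explains the gap, so a reader cannot tell which number the power statement belongs to.

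The power statement itself rests on one pair of rates, neither observed in the setting being studied. The control arm is once-daily treatment in Tunisia; the 60% is from twice-daily treatment of New World disease. That 60% sits near the Colombian intent-to-treat figure, yet 9.4 prescribes an analysis without early losses, for which the evaluable figure is the closer match. The occlusion arm is set at 95% on once-daily treatment, above the day-50 cure seen with twice-daily occlusion. Section 4.0 asks only whether once daily is as effective as twice daily.

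Finally, the trial is sized on cure but tested on cured or improved, with a test whose side is given only in 9.1.

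The comparison is meant to inform the arms of the Phase 3 study (4.0 and 7.0). Those who use the result need to know how much difference the trial can detect.

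**Working it through.** **Method.** Exact power of Fisher's test with n per arm, control rate p0 and occlusion rate p1:

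power = Σx Σy Bin(x; n, p0) · Bin(y; n, p1) · I[Fisher p(x, y) ≤ 0.05]

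Here x and y are the cured patients in each arm, and the one-sided p is the upper hypergeometric tail given x + y.

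**Step 1: the plan's own figure.** p0 = 0.60 and p1 = 0.60 + 0.35 = 0.95 (9.1).

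| n per arm | one-sided | two-sided |
|---|---|---|
| 19 | 77.8% | 68.3% |
| 20 | 80.8% | 71.6% |
| 24 | 89.0% | 82.1% |

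The stated 20 per arm is where one-sided power first reaches 80%. This also settles the meaning of the 35%: it is in percentage points. Read as a relative gain (0.60 × 1.35 = 0.81), power would be 31.7% at 20 per arm and 36.5% at 24.

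**Step 2: the control rate.** From 6.4.1, the evaluable rate is 33/51 = 64.7% (printed there as 66%). The intent-to-treat rate is 33/(51 + 5) = 33/56 = 58.9%. The 60% in 9.1 is near the second; the exclusion rule in 9.4 corresponds to the first.

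**Step 3: the occlusion rate.** The Old World study gives 91.8% cure at day 50 and 95.8% complete cure response. The assumed 95% lies between them.

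**Step 4: one-sided power with these rates.**

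| control v occlusion | 20 per arm | 24 per arm |
|---|---|---|
| 60% v 95% (as in 9.1) | 80.8% | 89.0% |
| 60% v 91.8% | 68.8% | 78.1% |
| 64.7% v 95% | 70.0% | 80.6% |
| 64.7% v 91.8% | 56.3% | 66.6% |
| 70% v 91.8% | 40.8% | 50.8% |
| 55% v 91.8% | 79.8% | 87.2% |

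The 55% and 70% are assumptions that bracket the control rate; the protocol gives no Old World rate for active drug without occlusion. Replacing either input alone leaves power near 80% at 24 per arm. Replacing both lowers it to about two thirds.

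**Step 5: a wider grid at 24 per arm, one-sided.**

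| control | v 90% | v 95% |
|---|---|---|
| 55% | 81.9% | 94.5% |
| 60% | 71.1% | 89.0% |
| 65% | 57.7% | 79.9% |
| 70% | 42.6% | 66.7% |
| 75% | 27.7% | 49.6% |

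**Step 6: the endpoint.** For the same lesions, the proportion cured or improved cannot be below the proportion cured. Counting improvement can therefore only raise the control rate and reduce the room for a difference. By how much cannot be computed, because the protocol gives no such rate for unoccluded treatment. All the power figures above are for cure.

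**The case against.** The strongest defence is that 9.1 is correct on its own terms, and that stands. It states its inputs, the number follows exactly from a one-sided Fisher test, and the 48 in the design sections raises power to 89.0%. Even a two-sided test has 82.1% power at 24 per arm.

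The rates can also be defended in part. The 95% is close to the 95.8% complete cure response. The 91.8% corresponds to 45/49, with an exact 95% confidence interval of about 80% to 98%, which includes 95%. On the control side, 2.0 cites a 25% placebo healing rate in the same area; adding the 30 points in the footnote gives 55%, and once-daily dosing could lower the rate too. So the control rate could lie below 60% as well as above it. The wording of 9.1 sets a target difference rather than a forecast, and 7.0 calls the study a pilot proof of concept.

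A reader might go further and say that a 35-point gain is impossible, since 73.2% + 35 = 108.2%. The documents do not support this. The 73.2% is vehicle under occlusion, and 2.0 suggests that occlusion itself may have helped healing. It is not an estimate for active drug without occlusion.

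A reader might also treat the list of 1 to 50 as a third required number. It is the length of a randomisation list, and a list longer than the sample contradicts nothing.

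None of this explains 40 against 48, the unstated side in 9.2 or the change of endpoint.

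**Conclusion.** Three things are wrong as written:

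- The required number contradicts itself (40 in 1.0 and 9.1; 48 in 3.0, 8.1 and 8.4).
- The trial is sized on cure but tested on cured or improved.
- The one-sided level in 9.1 is not carried into 9.2. This matters most at 20 per arm, where a two-sided test has 71.6% power on the plan's own rates.

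Beyond that, the single 80% is fragile rather than false. At 24 per arm, one-sided, the scenarios in step 4 range from 89.0% down to 50.8%. The lower values require both a control rate above 60% and an occlusion rate near 91.8%, and the 70% control rate is an assumption.

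It would be tempting to conclude that 9.1 is miscalculated, or that a null result is likely once the control rate passes about 70%. The first is not so. The second does not hold in general at 24 per arm: power is 66.7% for 70% against 95%, and 50.8% for 70% against 91.8%. Nor does the protocol contain a rule that a non-significant test would mean occlusion is unnecessary.

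The point calls for correcting the text. It does not undermine the design.

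**What to change.** 1. State one number, 24 + 24 = 48, in 1.0 and 9.1, matching 3.0, 8.1 and 8.4. If the extra eight patients are a dropout allowance, say so.
2. In 9.1, restate power at that number for a one-sided Fisher test at 0.05, and name the same side and level in 9.2.
3. Replace the single 80% with a short table of power over control rates of about 55% to 75% and occlusion rates of 90% to 95%. Say that the 60% comes from twice-daily New World treatment.
4. Size on the endpoint that 9.2 tests. If that is cured or improved, give assumed rates for it; if it is cure, amend 9.2.

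Reporting the difference between arms with its confidence interval would help interpretation but is secondary.

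The cost is protocol wording, with no patients beyond the 48 already planned. The downside is that the stated power becomes less favourable over part of the range.
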